11.3 Analysis of Surgical Endpoints

Surgical endpoints in patients randomized to extended PLND versus standard PLND will also be of interest, including operative time, whether or not nerve sparing was performed, morbidity and mortality (intra-operative, peri-operative, and at 90 days), length of hospital stay, underlying histology (pure urothelial versus mixed), lymph node counts and lymph node density, and whether adjuvant chemotherapy was received. These will be analyzed using generalized linear models, with confidence intervals and tests based on robust standard errors. Adjustments will be made for multiple comparisons. In patients randomized to the extended PLND arm, the proximal extent of node dissection will be analyzed in an exploratory manner. Also, the two arms will be compared for differences in time to local recurrence, and the time to retroperitoneal soft tissue recurrence using a log-rank test.

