An extended node dissection in patients undergoing cystectomy for bladder cancer may offer a survival benefit compared to a standard node dissection via more complete tumor eradication, improved staging and thus identifying patients who may benefit from adjuvant chemotherapy, or other theoretical mechanisms. In order to optimize the benefits of an extended node dissection through improved nodal staging, all patients with node metastasis will be strongly advised to receive peri-operative chemotherapy which is currently considered a standard of care in locally advanced urothelial bladder cancer. In addition and in accordance with standard of care, chemotherapy will be strongly recommended for patients found to have advanced pathologic stage (pT3-T4) at cystectomy. Failure to include this stipulation in the trial design could result in biased administration of adjuvant chemotherapy, influenced by which arm the patient was randomized to, and lead to non-informative results.

A poll of centers of excellence suggest that a 10-12% improvement in 3-year DFS (65-67%) for patients in extended lymphadenectomy would be meaningful and establish extended node dissection as the standard of care in this patient population

Since the introduction of MVAC chemotherapy in the 1980s, little progress has been made in improving survival for patients with advanced bladder cancer. Despite a significant improvement in overall survival with administration of peri-operative chemotherapy, the mortality rate for patients undergoing radical cystectomy for UCB approaches 50%. A properly performed lymph node dissection may provide a significant improvement in survival for these patients. Currently the boundaries of a pelvic node dissection for patients undergoing radical cystectomy for UCB are not clear and the urologic community has failed to define a standard template. The literature is replete with various proposed definitions. Defining, a standard nodal dissection for this disease is

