6.0 STRATIFICATION FACTORS

Patients will be randomized using a dynamic balancing algorithm (30) with stratification based on:

- a. Neoadjuvant chemotherapy: Cisplatin based, vs. Carboplatin based, vs. Other, vs. none.
- b. Clinical stage T2 vs. T3 or T4a. NOTE: Clinical stage is based on all of the following: TURBT(s) that determined the need for cystectomy, bimanual exam and cross sectional imaging.
- c. Zubrod performance status: 0-1 vs. 2.

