7.3 Adherence to Recommendations for Adjuvant Chemotherapy

For patients who did not receive neoadjuvant chemotherapy, post operative adjuvant chemotherapy for pT any, N+ or pT3-4, N0 is strongly recommended but not required and will be left up to the treating physician. The Study Chairs will review the records of all patients enrolled to assess adherence to this recommendation. Non-compliance with this recommendation will be addressed by inquiry with the site physicians and coordinators.

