11.0 STATISTICAL CONSIDERATIONS

11.1 Accrual Goal

We anticipate that 113 eligible patients will be randomized per year to this study on a group-wide basis. We will also assume that 10 percent of enrolled patients will be found to be clinically or pathologically ineligible and hence, not randomized so our Step 1 sample size will be inflated to account for this. Based on an extensive review of the contemporary literature (see [Section 2.0, Table 1](#)), we estimate that 3-year disease free survival (DFS) for patients at increased risk for pelvic and iliac node metastasis undergoing a standard pelvic lymphadenectomy is 55%. A poll of centers of excellence suggest that a 10-12% improvement in 3-year DFS (65-67%) for patients in extended lymphadenectomy would be meaningful and establish extended node dissection as the standard of care in this patient population. Assuming exponential survival, 5 years of patient accrual, 3 additional years of follow-up and a sample size of 564 eligible patients (282 per arm), the study has 85% power to detect a 28% reduction in the hazard rate of progression or death with extended lymph node dissection compared to limited

dissection (hazard ratio 0.72). This corresponds to an improvement in 3-year DFS from 55% to 65% or alternatively median DFS would be extended from 3.5 to 4.8 years if the DFS distributions are exponential. We will use a one sided stratified log rank test with $\alpha = 0.025$, and the analysis will be intent-to-treat.

Assuming an ineligibility rate of 10%, total accrual (eligible + ineligible patients) to the initial step is expected to be 620 patients.

As a secondary endpoint, overall survival is also of great interest. If extended lymph node dissection is found to be statistically significantly better than standard lymph node dissection with respect to DFS, then an analysis of the survival endpoint will follow. We will allow for three more years of follow-up after the primary analysis has been conducted to assess potential survival differences. If we assume that the standard arm has 5-year survival of 55% then we will have 83% statistical power to detect a hazard ratio of 0.72 (55% vs. 65% survival at 5 years) using a one-sided stratified logrank test with alpha=0.025.

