11.4 Analysis of Translational Medicine Endpoints

Aim: To identify the relationship between expression of markers of epithelial mesenchymal transition in the primary bladder tumor with local tumor stage, the burden of lymph node metastases, and the likelihood of disease recurrence among patients undergoing cystectomy for muscle invasive bladder cancer.

Tumor marker expression will be measured as a function of proportion of cells staining and intensity of staining (IHC studies) and/or relative level of mRNA expression (compared to internal controls). Associations between marker expression and nodal status (positive vs negative, low disease burden versus high disease burden), and neoadjuvant chemotherapy will be tested using chi square test. Kaplan Meier estimates of survival and DFS based on marker expression will be performed and corresponding survival and DFS curves will be compared using log rank testing. Cox proportional hazards regression analysis will be performed to estimate hazard ratios for progression free survival. Those analysis will be repeated, stratified by whether patients received

neoadjuvant and adjuvant chemotherapy. Where associations look different by strata, formal tests of interaction will be performed in order to assess markers associated with chemoresistance.

If we assume that 70% of patients will have adequate tissue samples available based on prior SWOG experience with surgical trials, then we will have 396 samples (198 per arm). The following table provides estimate of the minimally detectable hazard ratio for disease-free survival for those with the tissue marker of interest vs. those without. These calculations assume 5 years of accrual, 3 additional years of follow-up, median DFS of 3-year in those with the marker, a two-sided alpha=0.05 and 80% statistical power. Similar survival hazard ratios can be detected with two additional years of follow-up. These calculations also assume there is no interaction between the marker of interest and the randomized treatment assignment (type of lymph node dissection).

	Prevalence of Tissue Marker		
	10%	20%	30%
DFS Hazard Ratio for Those with versus Those without the Marker of Interest	1.82	1.57	1.50

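### Section 11.3 compares adjuvant chemotherapy between arms without stratifying by neoadjuvant chemotherapy; the comparison is valid, but stratifying it would sharpen the reported interval at no cost in data

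*Combined protocol and SAP*

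**What the plan says.** Section 11.3 names receipt of adjuvant chemotherapy as one of the surgical endpoints to be compared between arms: "whether adjuvant chemotherapy was received. These will be analyzed using generalized linear models, with confidence intervals and tests based on robust standard errors". The only adjustment it mentions is for multiple comparisons. It gives no covariate, stratum or effect measure.

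Section 6.0 states: "Patients will be randomized using a dynamic balancing algorithm (30) with stratification based on" three factors, the first being "Neoadjuvant chemotherapy: Cisplatin based, vs. Carboplatin based, vs. Other, vs. none". The other two are clinical stage and performance status.

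Section 7.3 ties adjuvant treatment to that first factor: "For patients who did not receive neoadjuvant chemotherapy, post operative adjuvant chemotherapy for pT any, N+ or pT3-4, N0 is strongly recommended". The recommendation is not binding, and the decision rests with the treating physician.

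For the primary endpoint the plan does stratify. Section 11.1 says "We will use a one sided stratified log rank test with" a one-sided level of 0.025, and adds that "the analysis will be intent-to-treat". Section 11.3 is silent on the matter.

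**The concern.** Section 2.0 explains why the protocol carries a chemotherapy recommendation at all: without one, the design "could result in biased administration of adjuvant chemotherapy, influenced by which arm the patient was randomized to", and the trial might not be informative. Because the decision still lies with the physician, the comparison of adjuvant use by arm is the trial's quantitative check on that risk. Readers of the DFS result will want it to be as precise as the data allow.

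The stratum most likely to predict adjuvant use is fixed before randomization, recorded, and balanced by the allocation. Balancing removes chance differences between arms in neoadjuvant use from the estimated arm difference. A robust standard error from a model without that factor does not know this and still includes the corresponding variation. The estimate is sound, but its reported uncertainty is overstated. The all-patient figure alone also does not show whether an imbalance arises among patients whom the recommendation covers or among those it does not.

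**Working it through.** **The plan's own figure.** The only precision statement for binary endpoints is in Section 11.2: a frequency can be estimated to within ± 6% with 282 patients per arm. At the worst case of 50%, 1.96 × √(0.25/282) = 5.8 points, which agrees. That figure concerns one frequency in one arm, not a difference between arms.

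**Inputs.**
- From the documents: 282 per arm (Section 11.1). A 50% neoadjuvant share is the illustrative layout in Section 11.4 (35% + 15%), which gives 141 per arm in each stratum.
- Assumed, because the documents do not give them: adjuvant use of 30% (standard) versus 40% (extended) without neoadjuvant treatment, and 5% or 10% in both arms with it. The test is two-sided at 0.05, before the multiplicity adjustment.

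The all-patient rates are then 17.5% versus 22.5% (5% case) or 20% versus 25% (10% case), a 5-point difference in each.

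**Variance of the arm difference.**
- Unadjusted: [p₀(1−p₀) + p₁(1−p₁)]/282.
  - 5% case: (0.1444 + 0.1744)/282 = 0.001130.
  - 10% case: (0.1600 + 0.1875)/282 = 0.001232.
- Stratified, each stratum weighted one half: ¼ × [(0.21 + 0.24)/141 + 2q(1−q)/141], where q is the rate after neoadjuvant treatment.
  - 5% case: ¼ × (0.45 + 0.095)/141 = 0.000966.
  - 10% case: ¼ × (0.45 + 0.18)/141 = 0.001117.

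| | 5% after neoadjuvant | 10% after neoadjuvant |
|---|---|---|
| Half-width, unadjusted | 6.59 points | 6.88 points |
| Half-width, stratified | 6.09 points | 6.55 points |
| Variance ratio | 1.17 | 1.10 |
| z, unadjusted to stratified | 1.48 to 1.60 | 1.42 to 1.49 |
| Power, unadjusted to stratified | 31.7% to 36.0% | 29.6% to 32.0% |

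The z values are the pooled two-proportion test and the Cochran-Mantel-Haenszel test.

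**True level of the unadjusted test.** With no arm difference (35% without and 5% or 10% with neoadjuvant treatment) and exact balance, the level is 2 × [1 − Φ(1.96 × √(p(1−p)/w))], where p is the overall rate and w the mean within-stratum variance.
- 5% case: p = 0.20, p(1−p) = 0.1600, w = (0.2275 + 0.0475)/2 = 0.1375; level 3.4%.
- 10% case: p = 0.225, p(1−p) = 0.1744, w = (0.2275 + 0.09)/2 = 0.1588; level 4.0%.

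**Simulation.** There were 6,000 runs per case with 564 patients, minimized over the three factors of Section 6.0. Assumed settings: biased coin 0.8; neoadjuvant types 80/15/5%; 35% T3–T4a; 8% performance status 2. Results for the 5% and 10% cases:
- Level: 3.6% and 4.1% unadjusted, against 4.8% and 5.2% stratified.
- Power: 30.9% and 28.5% unadjusted, against 36.3% and 32.1% stratified.

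A separate simulation, balanced on neoadjuvant status with 40% adjuvant use without and 5% with it in both arms, gave a level of 3.3% unadjusted and 5.4% stratified. Bias was negligible either way. The actual spread of both estimates was the same (standard deviation 0.0322), while the mean reported standard errors were 0.0351 and 0.0318. Under balancing, then, the point estimate hardly changes; the reported uncertainty does.

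**Other assumptions** (power by formula; 5% case, 10% case):

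| Scenario | Unadjusted | Stratified |
|---|---|---|
| 40% neoadjuvant use | 39.4%, 37.6% | 43.9%, 40.3% |
| 60% neoadjuvant use | 24.5%, 22.1% | 28.0%, 23.9% |
| 20% vs 30% without neoadjuvant | 38.3%, 34.6% | 41.0%, 35.7% |
| Neoadjuvant patients also differ by 2 points | 42.3%, 39.5% | 47.3%, 42.3% |
| Neoadjuvant patients also differ by 5 points | 58.6%, 55.3% | 63.7%, 58.3% |
| Base case at an illustrative 0.05/9 | 9.9%, 8.8% | 12.1%, 10.0% |

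Over neoadjuvant shares of 30–70%, adjuvant rates of 20–60% without and 2–10% with neoadjuvant treatment, the stratified variance is 0.55 to 0.985 of the unadjusted one. If the rates are equal in both strata (20% vs 25%), z is 1.42 either way and nothing is gained or lost.

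**Stratum estimates.** Without neoadjuvant treatment, the difference is 10 points with half-width 1.96 × √(0.45/141) = 11.1. With it, the half-width is 5.1 or 7.0 points.

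**The case against.** The planned comparison is valid, and a generalized linear model can take covariates, so silence is not a decision to leave them out. That is fair. But the text names none, so the choice remains open until after the data are seen.

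The gain is small and its size rests on assumed rates. This stands. If 20% of neoadjuvant patients also received adjuvant treatment, the half-width would move only from 7.36 to 7.24 points. After multiplicity adjustment, power is low with either analysis. In the base case, a test confined to patients without neoadjuvant treatment has more power (42%) than the stratified all-patient test, but it answers a narrower question than the one relevant to the intent-to-treat DFS comparison.

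Precision does not improve on every scale. With a logit link, on the base inputs, the standard error of the log odds ratio rises on adjustment (0.212 to 0.229, or 0.203 to 0.213) and the quantity becomes conditional, although the test still gains slightly. This stands, and it is why the effect measure has to be named.

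The protocol already guards against biased prescribing. The warning in Section 2.0 concerns a design without the recommendation, which is in place. The Study Chairs review every patient's adherence (Section 7.3), and the vanguard phase monitors consistency of adjuvant chemotherapy (Section 11.2). These are controls on conduct, however, and do not estimate the difference between arms.

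Clinical stage may also predict adjuvant use. It could be added, but neoadjuvant status is the factor that the recommendation itself turns on.

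**Conclusion.** The concern holds as an optional improvement. Run without a stratum, the comparison is unbiased but reports intervals that are somewhat too wide: by 0.5 or 0.3 points of half-width in the base case, with a true level of 3.4–4.0% instead of 5%, and 2 to 4 points of power forgone. The size depends on assumed neoadjuvant and adjuvant rates. The direction did not reverse in any scenario examined, and with equal rates in both strata the two analyses coincide. The primary DFS test, the sample size and the trial's error rates are unaffected. A split by neoadjuvant use can show where a difference arises. It cannot separate intended use prompted by better staging from biased prescribing, and the interval in the no-neoadjuvant stratum is wide.

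**What to change.** Keep the all-patient comparison as the main one and add one sentence to Section 11.3: the arm difference in receipt of adjuvant chemotherapy is estimated as a risk difference stratified by neoadjuvant chemotherapy (any versus none). On this scale the all-patient quantity is unchanged, and two levels avoid sparse carboplatin and other-regimen cells. Report the arm difference with a 95% confidence interval in each of the two strata as description, without a test. Do not condition on pathologic T or N stage, because extended dissection can itself change the nodal stage found.

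The cost is one sentence and two table rows. No new data are needed: neoadjuvant status is recorded for randomization, and Section 11.4 already plans marker analyses split by chemotherapy ("Those analysis will be repeated, stratified by whether patients received" neoadjuvant and adjuvant treatment).

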5.1 Disease-related Criteria (Step 1)

- a.** Patients must have histologically-proven (T2, T3, or T4a) urothelial carcinoma of the bladder (UCB) that requires primary radical cystectomy for definitive treatment. Patients must not have clinical stage consistent with a low-risk of node metastasis (CIS only, T1). Patients with a T4b (fixed lesion) are not eligible for this study.

NOTE: Patients with predominant urothelial carcinoma with elements of adenocarcinoma, squamous cell carcinoma, micropapillary or minor components of other rare phenotypes are eligible. Patients with predominantly small cell, squamous cell, or adenocarcinoma histologies are not eligible. Patients with other non-urothelial cancers are not eligible (e.g., sarcoma, lymphoepithelial, nested variant).

Clinical stage is based on all of the following: TURBT(s) that determined the need for cystectomy, bimanual exam and cross sectional imaging.

- b.** There must be plans for the cystectomy and lymph node dissection (LND) to be performed within 28 calendar days following registration. Laparoscopic surgery is not allowed.
- c.** Surgery must be planned to be performed by a pre-approved, study-specific credentialed surgeon (see [Section 12.1](#) for credentialing process). The registering physician MUST be the pre-approved, credentialed surgeon intended to perform the assigned procedure.
- d.** Patients must not have undergone a prior partial cystectomy for invasive bladder cancer. Patients must not have received any prior pelvic surgery that would obviate a complete extended lymphadenectomy (e.g. aorto-femoral/iliac bypass) or for whom the surgeon feels that their ability to perform a standard or extended pelvic node dissection would be compromised.

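### Section 11.3 names no covariates for the surgical-endpoint models; adding the three balancing factors and, for continuous endpoints that vary by surgeon, the surgeon would narrow intervals at almost no cost

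*Combined protocol and SAP*

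**What the plan says.** Section 11.3 lists operative time, nerve sparing, morbidity and mortality, length of stay, histology, node counts and density, and receipt of adjuvant chemotherapy. On method it says "These will be analyzed using generalized linear models, with confidence intervals and tests based on robust standard errors", followed by "Adjustments will be made for multiple comparisons". It names no covariates, link function or summary measure. The two recurrence-site comparisons in the same section, local recurrence and "time to retroperitoneal soft tissue recurrence using a log-rank test", are not described as stratified.

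Section 6.0 says "Patients will be randomized using a dynamic balancing algorithm (30) with stratification based on" three factors:
- "Neoadjuvant chemotherapy: Cisplatin based, vs. Carboplatin based, vs. Other, vs. none"
- "Clinical stage T2 vs. T3 or T4a"
- "Zubrod performance status: 0-1 vs. 2"

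Neither surgeon nor site is among them. Sections 11.1 and 11.2 specify stratified log-rank tests for DFS and OS, without listing the strata there.

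Section 5.1c says "The registering physician MUST be the pre-approved, credentialed surgeon intended to perform the assigned procedure". Section 7.1 places randomization during surgery, after exploration. The registering surgeon is therefore a baseline variable.

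**The concern.** The protocol itself treats surgical practice as variable. Section 2.0 describes wide differences between urologists in the extent of dissection and the number of nodes removed, and Section 7.2b leaves dissection above the aortic bifurcation to the surgeon. Variation between surgeons that is left in the residual inflates the standard error of the arm difference. Robust standard errors protect validity but do not recover that precision.

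Section 2.0 also says that added morbidity might outweigh any benefit and that prospective data are lacking. The models in 11.3 carry the trial's comparison of surgical burden, so avoidable imprecision matters there, particularly for operative time and length of stay. Leaving the covariates open also allows the model to be chosen after the data are seen.

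**Working it through.** **1. The plan's own precision figure.** Section 11.2 states that morbidity frequencies can be estimated to within 6 percentage points with 282 patients per arm.
- One arm, p = 0.5: 1.96 × √(0.25/282) = 5.84 points. The stated figure reproduces.
- It describes one arm, not the contrast. For the difference between arms, 1.96 × √(2p(1−p)/282) gives 8.3 points at p = 0.5, 7.6 at 0.3 and 5.0 at 0.1, before any multiplicity adjustment.

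**2. Inputs for the surgeon question.** From the documents: 564 patients, 282 per arm (11.1), and 15 surgeons polled before the protocol was developed (2.0). Not in the documents: the ICC and the final number of surgeons. Assumed: ICC 0 to 0.5, and 15 to 60 surgeons.

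**3. Large-sample formula, continuous endpoint.** For an outcome with SD 1, the unadjusted standard error is 2/√564 = 0.084. Removing the surgeon component multiplies it by √(1−ICC): 0.949 at ICC 0.1, 0.894 at 0.2, 0.837 at 0.3 and 0.707 at 0.5. This is an upper limit on the gain, because it ignores the finite number of surgeons and uneven arms within surgeon.

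**4. Simulation of a surgeon random intercept** (REML, unequal surgeon volumes, 1,000 runs per setting). Adjusted/unadjusted standard error:

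| ICC | 15 surgeons | 36 surgeons | 60 surgeons |
|---|---|---|---|
| 0 | 0.999 | 0.999 | 0.999 |
| 0.1 | 0.963 | 0.967 | 0.971 |
| 0.2 | 0.914 | 0.917 | 0.924 |
| 0.3 | 0.859 | 0.864 | 0.872 |
| 0.5 | 0.739 | 0.737 | 0.747 |

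A separate run of the same design gave about 1.00, 0.97, 0.92, 0.87 and 0.75. Taking these rounded values, the reductions are 3%, 8%, 13% and 25% for ICC 0.1 to 0.5. As equivalent sample size, (ratio)⁻² gives 1.06, 1.18, 1.32 and 1.78.

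**5. Surgeon as a fixed effect instead.** At ICC 0 the ratio is 1.013, 1.027 and 1.059 with 15, 30 and 60 surgeons, so there is a small loss. At ICC 0.1 it is 0.965, 0.976 and 1.003. The random intercept avoids most of this cost.

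**6. Balancing factors.** Without them the interval is wider by 1/√(1−R²) − 1: 0.5% at an assumed R² of 0.01, 2.6% at 0.05 and 5.4% at 0.10.

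**7. Binary endpoints** (surgeon SD 0.5 to 1.0 on the logit scale, baseline risk 10% to 50%, 15 or 30 surgeons, surgeon fixed effects). The standard error ratio for the risk difference is 0.93 to 1.01. For the log odds ratio it is 1.04 to 1.16, so that interval widens; the conditional odds ratio is also a different estimand from the unadjusted one.

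**8. Validity.** Simulated coverage of the unadjusted 95% interval for continuous outcomes was 0.93 to 0.96.

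**The case against.** The strongest reply is that 11.3 is silent, and silence is not a decision. A reader might infer that the plan leaves out the balancing factors and the surgeon. The text does not say so: a generalized linear model can carry covariates, and none is excluded. What can be said is that they are not specified.

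A reader might also infer that unadjusted intervals would be wrong. For surgeon they would not be. Surgeon is not a balancing factor, so an unadjusted interval properly reflects chance imbalance between surgeons, and its coverage is about nominal. The argument that the interval overstates the uncertainty applies only to the three balancing factors, where the effect is probably small.

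The inference that power for complications is being lost is weak too. In one simulation (36 surgeons, odds ratio 1.6, surgeon fixed effects on the risk-difference scale, surgeon SD 0.3 to 0.5), power at 20% baseline risk was 65.6% unadjusted against 63.7% adjusted at the lower SD, and 65.0% against 64.1% at the higher. A surgeon-stratified test gained only when surgeons differed strongly: at SD 1.0 and about 30% baseline risk, power rose from 82% to 88% with 15 surgeons and from 83% to 87% with 36.

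It is also fair to say that node count may not need the precision. Section 2.0 cites means of 25 against 14 nodes in a non-randomized series, a contrast that 282 per arm is unlikely to miss. Histology and adjuvant chemotherapy are not plainly driven by the surgeon. Finally, the plan sets no power target for these comparisons, so none is missed.

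All of this limits the point. It does not remove it: the variables are recorded, the method is better for the continuous endpoints, and a random intercept costs essentially nothing if surgeons turn out not to differ.

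**Conclusion.** The point holds as one of efficiency and specification in secondary analyses. Section 11.3 specifies neither the balancing factors nor the surgeon. If the models are fitted with arm alone, intervals for operative time, length of stay, node count and node density remain valid but are wider than they need be. A surgeon random intercept would reduce the standard error by about 3%, 8%, 13% and 25% at ICC 0.1, 0.2, 0.3 and 0.5. These sizes rest on an assumed ICC, an assumed 15 to 60 surgeons, and patient-level randomization that usually puts each surgeon in both arms.

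The balancing factors probably add under 3% in width if their R² is 0.05 or less. Little or no gain should be claimed for complications and other binary endpoints, including histology and receipt of adjuvant chemotherapy. A reader might carry the concern over to DFS; that is not supported, because the primary test is already a stratified log-rank test.

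**What to change.** Add to Section 11.3, before the arms are compared:
- Every model includes the three Section 6.0 balancing factors as covariates.
- Models for operative time, length of stay, node count and node density also include a random intercept for the registering surgeon.
- Binary endpoints are reported as a standardized risk difference adjusted for the balancing factors, with a simpler model named in advance for rare events.
- The link and summary measure are stated for each endpoint.
- Post-randomization variables are excluded as covariates.

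It would help to say in the same place whether the two recurrence-site log-rank tests are stratified.

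The cost is a few sentences and slightly more analysis work. No new data are needed: the balancing factors are used at randomization and the surgeon is recorded at registration. The main downside is possible non-convergence for rare outcomes, which the simpler model covers.
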